#### **Methods**

##### *Rome III criteria for IBS*

Recurrent abdominal pain or discomfort at least 3 days/month in the last 3 months associated with two or more of the following:

1. Improvement with defecation
2. Onset associated with change in frequency of stool
3. Onset associated with change in form (appearance) of stool.

Criteria fulfilled for the last 3 months with symptom onset at least 6 months prior to diagnosis.

Diarrhea-predominant IBS is defined by the presence of loose (mushy) or watery stools at least 25% of times and hard or lumpy stool <25% of times (in the absence of anti-diarrheal or laxative use).

Constipation-predominant IBS: hard or lumpy stools  $\geq$ 25% and loose (mushy) or watery stools <25% of bowel movements.

Mixed IBS: hard or lumpy stools  $\geq$ 25% and loose (mushy) or watery stools  $\geq$ 25% of bowel movements.

Unsubtyped IBS: insufficient abnormality of stool consistency to meet criteria for IBS-C, D, or M.

The validated Bristol Stool Form scale will be used to determine the participants usual stool consistency.

#### *Criteria for PI-IBS*

Acute onset of symptoms of IBS subsequent to two or more of the following: 1) fever, 2) vomiting, 3) diarrhea.

### **STUDY PROCEDURES:**

This study will be conducted at the University of Utah and the VA Medical Center. Information collected at the VA will be stored at the VA. For purposes of statistical analysis the information from the VA will be de-identified and sent to the University of Utah.

All patients will have a complete blood count, comprehensive biochemical profile (including serum calcium), thyroid-stimulating hormone (TSH), tissue transglutaminase antibody (TTG), C- reactive protein, and stool examination for electrolytes (optional), ova and parasite, C.difficile toxin (not required if stool is formed), Calprotectin or lactoferrin, and Giardia antigen. These tests will not be repeated if they were collected in the last 6 months. Blood and stool samples will be collected for storage if the patient consents. Flexible sigmoidoscopy and biopsy of the colonic mucosa will be performed in all patients at the beginning of treatment. Patients with red flag symptoms (onset in older than >50 years, progressive or non-fluctuating symptoms, unexplained weight loss, rectal bleeding or anemia, family history of colon cancer, fever, abnormal examination or laboratory tests) will have colonoscopy and biopsy. Patients with structural, biochemical, or infective disorders will be excluded from the study. A flexible sigmoidoscopy or colonoscopy will not be done if an acceptable biopsy was completed within 5 years. If the procedures are done a biopsy will be collected for storage.

#### *Questionnaires*

##### *Bowel Disease Questionnaire*

The Bowel Disease Questionnaire (BDQ) will be used to identify patients with IBS. The BDQ has been modified to include Rome III criteria for functional bowel disorders. We have used the BDQ and the modified version in our previous studies.

##### *Bowel Symptom Scale (BSS)*

BSS is a validated IBS outcome measure which consists of 100-mm visual analog scales related to each symptom of IBS (pain/ discomfort, bloating, constipation, diarrhea) and an overall severity scale. All questions contribute equally to the total score, which ranges from 0-400. Similarly reflux disease questionnaire (RDQ) measures change in upper gastrointestinal symptoms before and after treatment.

##### *Psychological Symptom Questionnaire*

The BSI-18 questionnaire (Brief Symptom Inventory, a short form of symptom check list-90-revised, SCL-90-R) will be used. The BSI-18 has 18 items, six each on the somatization, depression, and anxiety dimensions. The global severity index represents the global or total score, which summarizes the respondent's overall level of distress. Each item response is scored 0-4. This questionnaire can be completed in 4 minutes. The psychological symptoms and composite scores from BSI-18 test correlate highly (i.e.>0.90) with SCL-90-R.

##### *IBS-QOL Questionnaire*

The disease-specific IBS-QOL will be used for evaluation of subjects QOL. The IBS-QOL is a validated disease specific quality of life questionnaire for use in patients with IBS. It has 34 items and measures 8 domains found to be relevant to patients with IBS: dysphoria, interference with activity, body image, health worry, food avoidance, social reaction, sexual, and relationships. The IBS-QOL has high internal consistency and high reproducibility. IBS-QOL has been shown to be sensitive to treatment response in patients with IBS.

##### *Nepean Dyspepsia Index*

The Nepean Dyspepsia Index (NDI) will be used to evaluate how a patient's life and daily activities are affected by their stomach problems.

#### *Treatment Schedule*

This study will compare mesalamine two (Lialda®) 1.2 gm tablets orally daily to placebo in 68 patients with diarrhea predominant PI-IBS. The patients will be consented and enter into the screening which can last up to 8 weeks. This will be followed by an 8 week treatment period.

Patients will be re-consented to the newest version of the consent form if changes have been made while they are enrolled on the study. The patient may not be rescreened if there is no change in patient's symptoms if they are outside the screening window.

All patients will fill out the following questionnaires:

- 1) The Bowel Symptom Scale (BSS) at the beginning, at 4 weeks and at the end of the study period to assess any change based simply on admission to the trial.
- 2) The BSI-18 at the beginning of the screening period.
- 3) The IBS-QOL at the beginning, at 4 weeks and end of treatment.
- 4) The Nepean Dyspepsia Index at the beginning, 4 weeks and end of treatment as well as during the mail-in/phone call visits. BDQ (Bowel Disease Questionnaire) at screening.

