#### Time Line

##### *Location of Study*

This study will be performed at the University of Utah Hospital and Clinics and the VA Medical Center.

*Time Table of study:* Approximately 1 Years from the start of patient recruitment

Subject recruitment will start immediately upon IRB approval and continue throughout the duration of the study. We estimate that 50% of recruited patients will qualify for enrollment. Sixty-eight patients with diarrhea-predominant or mixed IBS (with diarrhea as predominant symptom) will be enrolled at the rate of 1-2 per week. The estimated dropout rate is 10%, leaving 64 patients to study. This population will include but not be limited to returned missionaries. We have previously worked with missionaries who have high prevalence of PI-IBS.

*Study visits* (Table 1. Figure 1.)

First visit:

Orientation to the study and informed Consent

Inclusion/Exclusion check

History and physical examination,

Questionnaires: BDQ, IBS-QOL, BSI-18, BSS, Nepean Dyspepsia Index (NDI)

Blood and stool tests (not repeated if done in past 6 months unless there has been an alteration in the symptoms)

Collection of stool sample for storage (if consent is given)

Urine pregnancy Test for women of child bearing potential

Instructions to complete 2 week stool diary during 8-week run in period

Second visit:

Flexible sigmoidoscopy/ colonoscopy with biopsy, if indicated (not repeated if performed during last 5 years, results within normal limits and no change in symptoms)

Third visit

Subjects will be randomly assigned to either two Lialda 1.2gm tablets daily or two placebo tablets daily according to a block randomization schedule generated by the statistician. Medicines will be provided by and dispensed at the Pharmacy. Medication may be mailed at patients' convenience and they will be informed on dosing and storage of medication by telephone.

Mail-in/ telephone visit

Patients will be asked to fill BSS IBS-QOL and NDI at week 4 of the 8 week treatment either by mail or on telephone.

Fourth visit

End of treatment- Questionnaires-BSS, IBS-QOL, and NDI and physical examination

Study drug count

Return all unused study drug and the study drug bottle(s)

**Standard of Care vs. Research-Related Procedures:** all procedures for this study are research-related.

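### The only scheduled pre-treatment BSS, IBS-QOL and NDI fall at Visit 1, up to 8 weeks before dosing, and baseline is undefined, so the analysed change can span 8 to 16 weeks

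*Combined protocol and SAP*

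**What the plan says.** All references are to the combined protocol and SAP.

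- **Treatment Schedule, duration.** "The patients will be consented and enter into the screening which can last up to 8 weeks"; an 8-week treatment period follows.
- **Treatment Schedule, questionnaires.** The BSS is due as follows: "The Bowel Symptom Scale (BSS) at the beginning, at 4 weeks and at the end of the study period", with the stated purpose "to assess any change based simply on admission to the trial". IBS-QOL and NDI are also placed at an unspecified beginning, at 4 weeks and at the end of treatment. Two other forms are dated more exactly: "The BSI-18 at the beginning of the screening period" and "BDQ (Bowel Disease Questionnaire) at screening".
- **Time Line, study visits.** The first visit lists "Questionnaires: BDQ, IBS-QOL, BSI-18, BSS, Nepean Dyspepsia Index (NDI") and "Instructions to complete 2 week stool diary during 8-week run in period". No questionnaire is listed at the second or third visit. At the third visit, "Subjects will be randomly assigned to either two Lialda 1.2gm tablets daily or two placebo tablets daily according to a block randomization schedule". BSS, IBS-QOL and NDI return at week 4 of treatment, by mail or telephone, and at the fourth visit.
- **Study Procedures table.** The three forms are marked at Visit 1, the week 4 contact and Visit 4. They are blank at Visit 3, the column for the start of treatment.
- **Study End-points.** The primary endpoint is improvement in overall BSS once 8 weeks of treatment are complete.
- **Sample Size.** The key between-arm comparison is of change between baseline and treatment end, by t-test, or by Wilcoxon test if data are highly skewed. The primary analyses are described as unadjusted. Mixed effects regression is also named, without saying whether the baseline score enters as a covariate or as a response.
- **Statistical section, after Sample Size.** IBS-QOL is said to be collected every 4 weeks, and a linear mixed model is to assess trends such as a linear divergence between arms.

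**The concern.** The primary endpoint is framed around 8 treated weeks, but the visit schedule supplies a starting score that may be up to 8 weeks old when treatment begins. Three things follow if that score serves as baseline.

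- Change within an arm mixes drift during the untreated run-in with change on treatment. With no score at treatment start the two cannot be separated, although the plan shows an interest in change caused merely by entering the trial.
- A linear trend model needs a time for each observation. The first interval is not a fixed 4 weeks, and the plan does not say where on the time axis the Visit 1 score sits.
- An older score may correlate less with the week 8 score. That would cost precision, mainly in an unadjusted test on change.

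**Working it through.** **Timing.** Inputs: screening of 0 to 8 weeks and treatment of 8 weeks (Treatment Schedule), with questionnaires at weeks 4 and 8 of treatment (visit list and table).

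- First score at treatment start: interval to week 4 = 4 weeks; span to week 8 = 8 weeks.
- First score at Visit 1 with *s* weeks of screening: interval to week 4 = *s* + 4; span to week 8 = *s* + 8. For *s* = 2, 4 and 8 the spans are 10, 12 and 16 weeks. The longest first interval is 8 + 4 = 12 weeks.

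If the run-in is a fixed 8 weeks, as the visit list words it, every patient has 16 weeks. If it can last up to 8, the span varies by patient.

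**Do the sections conflict?**

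- *IBS-QOL: yes.* Collection every 4 weeks cannot be squared with a first score at Visit 1 unless screening time is negligible.
- *BSS and NDI: not shown.* The 4-week statement does not mention them. The more exact dating of the BSI-18 and BDQ hints that the other forms belong to treatment start. The BSS line, however, refers to the study period and to trial admission, which fits Visit 1 equally well.

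**The plan's own sample size.** Inputs (Sample Size section): mean 183, SD 65, 25% change, two-sided alpha 0.05, 80% power. The difference is 0.25 × 183 = 45.75. Then n = 2(1.960 + 0.842)² × 65² / 45.75² = 31.7, so 32 per arm, as stated. Power at 32 per arm is 80.4% by the normal approximation and 79.1% by the t distribution.

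**Change score against baseline adjustment.** The documents give no correlation ρ between baseline and week 8, so a range is assumed, with SD 65 at both times.

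- Change score: SD = 65√(2(1 − ρ)). This equals 65 only at ρ = 0.5.
- Adjusted for baseline: SD = 65√(1 − ρ²), tested on 61 degrees of freedom, with allowance for estimating the slope and for chance baseline imbalance.

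Power at 32 per arm, difference 45.75, noncentral t:

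| Assumed ρ | SD, change | Power, change | SD, adjusted | Power, adjusted |
|---|---|---|---|---|
| 0.4 | 71.2 | about 72% | 59.6 | about 85% |
| 0.5 | 65.0 | about 79% | 56.3 | about 89% |
| 0.6 | 58.1 | about 87% | 52.0 | about 93% |

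At ρ = 0 adjusted power is about 78.5%, slightly below the 79.1% found when the cost of estimating the slope is ignored.

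The gap between the two power columns is the gain from adjustment and applies wherever baseline is taken. It is not an effect of timing. Naming a mixed model does not settle the matter. With complete data and visit as a category, its week 8 contrast matches the change score if baseline is a response with free arm means, and the adjusted result if baseline is a covariate.

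**The case against.** The visit list and the table agree with each other and supply exactly one pre-treatment BSS, so on that schedule baseline can only mean Visit 1. One sentence saying so, plus a correction to the IBS-QOL interval, would remove the ambiguity. The objectives and key comparisons are between arms, and within-arm change is not a listed endpoint. Figure 1, the flow chart, is not shown in the text available and might mark baseline.

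Much of this stands. The statement that baseline is undefined is limited to the visible text, and the omission could be cured by wording alone. Wording alone would still leave a starting score up to 8 weeks older than the treatment period that the endpoint describes, with no means of separating run-in change.

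Three stronger readings are tempting, and the documents support none of them.

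- *The sections contradict each other for all three instruments.* The contradiction is shown for IBS-QOL only.
- *The treatment comparison is biased.* Randomisation follows screening, so both arms share the run-in on average.
- *The early score costs power, for example from 87% to 72%.* Those figures belong to assumed correlations of 0.6 and 0.4. Nothing in the documents ties screening length to any fall in correlation, and if there is none, there is no loss.

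**Conclusion.** The point holds as a gap in definition and schedule that is cheap to close. As scheduled, the only pre-treatment BSS, IBS-QOL and NDI come at Visit 1, baseline is not defined in the visible text, and the analysed change can cover 8 to 16 weeks, with a first interval of 4 to 12 weeks. There is a true contradiction for IBS-QOL and ambiguity for BSS and NDI. The between-arm contrast is unbiased, and the planned 32 per arm (68 in total) is unaffected.

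The timing figures come directly from the documents. Any loss of precision from timing cannot be computed from them. The power figures rest on assumed correlations of 0.4 to 0.6 and an equal SD of 65 at both times. They support a separate conclusion: adjusting for a baseline score that is already being collected outperforms the unadjusted test on change across that range.

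**What to change.** 1. **Adjust for baseline.** State that the primary week 8 BSS comparison includes baseline BSS as a covariate, in place of the unadjusted t-test on change. This costs only text.
2. **Collect the forms before dosing and define baseline.** Obtain BSS, IBS-QOL and NDI at Visit 3 before the first dose, by mail or telephone if needed. Define these as baseline, with the Visit 1 scores as the stated fallback, and otherwise use Visit 1 to report run-in change separately. The cost is a small amendment, one extra set of self-completed forms per patient, and a check that they precede dosing, which takes some care when medication is mailed. The mail and telephone route already exists at week 4, so no extra visit is required. The fallback brings back mixed timing for the patients who need it, so report how many do.
3. **Reconcile the text.** Make the Treatment Schedule, the visit list, the Study Procedures table and the IBS-QOL statement in the statistical section agree on when the first scores are taken and how time is counted in the mixed model.

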#### Drug, Dose and Duration Rationale

Mesalamine with MMX (Multi Matrix System) technology (Lialda®) will be used for this study. This is a novel oral, high strength (1.2 gm/tablet) formulation of 5-ASA designed for once or twice daily administration. Lialda has been shown to be well tolerated for the treatment of mild to moderate ulcerative colitis. Previous studies have shown that clinical and endoscopic remission with 2.4 and 4.8 gm/ day was similar. Therefore the 2.4gm once daily dose will be used for this study. A placebo capsule will be provided by the makers of Lialda, Shire Pharmaceuticals, Inc. All study medication will be stored and dispensed at the University of Utah and VA pharmacies.

#### Assessment of Compliance

Every subject will be evaluated so that they are at least 80% compliant for continuous dosing of medication by pill count. Adverse reactions will be assessed. Patients will be called by the study coordinator every two weeks during the 8 week treatment period to check for medication compliance.

#### Concomitant Medications

All concomitant medications will be recorded. Drugs which affect the gastrointestinal motility will not be allowed during the study unless the patient has been on a stable dose for >1 month and symptoms are still persisting. - The following medications will be prohibited: oral anti-cholinergics (dicyclomine, hyocymine, and propantheline), narcotics, tramadol, colchicine, misoprostol, antacids, antidiarrheal agents, bismuth compounds and laxatives.

#### Time Line

##### *Location of Study*

This study will be performed at the University of Utah Hospital and Clinics and the VA Medical Center.

*Time Table of study:* Approximately 1 Years from the start of patient recruitment

Subject recruitment will start immediately upon IRB approval and continue throughout the duration of the study. We estimate that 50% of recruited patients will qualify for enrollment. Sixty-eight patients with diarrhea-predominant or mixed IBS (with diarrhea as predominant symptom) will be enrolled at the rate of 1-2 per week. The estimated dropout rate is 10%, leaving 64 patients to study. This population will include but not be limited to returned missionaries. We have previously worked with missionaries who have high prevalence of PI-IBS.

*Study visits* (Table 1. Figure 1.)

First visit:

Orientation to the study and informed Consent

Inclusion/Exclusion check

History and physical examination,

Questionnaires: BDQ, IBS-QOL, BSI-18, BSS, Nepean Dyspepsia Index (NDI)

Blood and stool tests (not repeated if done in past 6 months unless there has been an alteration in the symptoms)

Collection of stool sample for storage (if consent is given)

Urine pregnancy Test for women of child bearing potential

Instructions to complete 2 week stool diary during 8-week run in period

Second visit:

Flexible sigmoidoscopy/ colonoscopy with biopsy, if indicated (not repeated if performed during last 5 years, results within normal limits and no change in symptoms)

Third visit

Subjects will be randomly assigned to either two Lialda 1.2gm tablets daily or two placebo tablets daily according to a block randomization schedule generated by the statistician. Medicines will be provided by and dispensed at the Pharmacy. Medication may be mailed at patients' convenience and they will be informed on dosing and storage of medication by telephone.

Mail-in/ telephone visit

Patients will be asked to fill BSS IBS-QOL and NDI at week 4 of the 8 week treatment either by mail or on telephone.

Fourth visit

End of treatment- Questionnaires-BSS, IBS-QOL, and NDI and physical examination

Study drug count

Return all unused study drug and the study drug bottle(s)

**Standard of Care vs. Research-Related Procedures:** all procedures for this study are research-related.

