## **STATISTICAL METHODS, DATA ANALYSIS AND INTERPRETATION:**

### **Sample Size**

The sample size for this trial is based on primary end-point of overall improvement in BSS. A previous IBS treatment trial reported baseline BSS of  $183 \pm 65$ . To detect 25% change in BSS, 32 patients in each group will provide 80% power using two-sided alpha 0.05 comparisons. Assuming 5% drop out rate, we would require a total of 68 patients ( $n=34$  in each group). Assuming proportional estimates for the individual symptoms of IBS, a similar power will be achieved with this sample size.

The Lialda treated group will be compared to the placebo group on improvement in the BBS global symptoms of IBS (continuous scale, range 0 to 400) and BBS individual symptoms of IBS (continuous scales, range 0 to 100). Given the repeated measurements on continuous outcomes, the data will be analyzed with mixed effects linear regression.

Primary analysis will be based on intention to treat. Exploratory analyses assessing "compliers" will also be reported. We will compare the results of placebo and Lialda treated group. The key comparisons between treatment arms will assess changes from baseline to end of treatment using parametric approaches such as the t- test and, when data is highly skewed, nonparametric approaches such as the Wilcoxon test. We note that it is feasible to construct confidence intervals as well as significance tests in the setting of nonparametric comparisons. For some of the secondary efficacy approaches, such as those with binary/ categorical outcomes, follow-up status will be compared between treatment arms using the chi-squared test of the Mantel-Haenszel chi-square for ordered categorical outcomes. Exact versions of these tests will be performed when cell sizes are excessively small.

In addition to the unadjusted primary analyses we will perform exploratory analyses which will use the logistic regression model for binary outcomes, and the linear regression model for continuous outcomes (transformations or categorization may be necessary for the cell count variables). We expect that psychological factors may affect the response to treatment and therefore will do pre-study psychological analysis and will control for them while evaluating response to treatment.

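### The Time Line's 10% dropout leaves about 61 of 68 patients, not 64; the 64 and the 80% power go with the 5% rate in the Sample Size section

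*Combined protocol and SAP*

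**What the plan says.** The Time Line section (under Location of Study) sets enrolment at 68: "Sixty-eight patients with diarrhea-predominant or mixed IBS" "will be enrolled at the rate of 1-2 per week". It then states: "The estimated dropout rate is 10%, leaving 64 patients to study".

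The Sample Size section starts from the evaluable number: "To detect 25% change in BSS, 32 patients in each group will provide 80% power", with two-sided alpha 0.05. The input is introduced by "A previous IBS treatment trial reported baseline BSS of" 183 ± 65. It then adds an allowance for attrition: "Assuming 5% drop out rate, we would require a total of 68 patients", that is, 34 in each group.

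Both sections go from 68 enrolled to 64 remaining, one at 10% and the other at 5%. Nothing elsewhere in the document reconciles the two rates.

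**The concern.** The Time Line sentence does not agree with its own numbers, and its rate is twice the one used to set the enrolment target. A reader cannot tell which attrition the investigators expect. If it is 10%, the trial would finish with fewer evaluable patients than it says, and the 80% power was obtained with a lower dropout rate than the one expected. Anyone monitoring progress would also not know whether 10% attrition is on plan or double the plan.

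**Working it through.** **Inputs.** From the Time Line: 68 enrolled, 10% dropout, 64 remaining. From Sample Size: 32 per group (64 in total), 80% power, two-sided alpha 0.05, baseline BSS 183 with SD 65, 25% change, 5% dropout, 68 in total (34 per group).

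**Step 1: reproduce the plan's 32 per group.** The section does not say what the 25% change is a change in. Read as a between-arm difference of 0.25 × 183 = 45.75 points with SD 65, the normal approximation gives

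n = 2 × (1.96 + 0.8416)² / (45.75/65)² = 31.7, so 32 per group.

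This matches the plan, so that reading is used below.

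**Step 2: reproduce the 68.**

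- At 5%: 64/0.95 = 67.4, rounded up to 68 (34 per group). In reverse, 68 × 0.95 = 64.6. The Sample Size derivation holds.
- At 10%: 64/0.90 = 71.1, which would be 72 (36 per group), not 68.

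**Step 3: check the Time Line figure.** 68 × 0.90 = 61.2, about 61. Rounding 30.6 per arm up to 31 gives 62, still not 64. Going from 68 to 64 is a loss of 4/68 = 5.9%.

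**Step 4: effect on power, counting completers only.** For the normal approximation, power = Φ(45.75 / (65 × √(1/n1 + 1/n2)) − 1.96). The t-test column uses the noncentral t with n1 + n2 − 2 degrees of freedom.

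| Completers per arm | Total | Normal | t-test |
|---|---|---|---|
| 34 / 34 (no loss) | 68 | 82.7% | 81.6% |
| 32 / 32 (as planned) | 64 | 80.4% | 79.1% |
| 31 / 31 | 62 | 79.1% | 77.8% |
| 31 / 30 | 61 | 78.5% | 77.1% |
| 34 / 27 (all losses in one arm) | 61 | 77.9% | 76.6% |

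Against 32/32, the loss at 61 patients is 1.9 points (normal) or 2.0 (t-test) when dropouts are nearly balanced. It is 2.4 or 2.5 points when all of them fall in one arm.

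**The case against.** The best counter-argument is that the consequence is negligible. The choice between the normal approximation and the t-test alone moves the plan's own 32/32 power by 1.3 points (80.4% against 79.1%), and at 31 per arm the dropout effect is no larger than that (80.4% to 79.1%). The primary analysis is also by intention to treat, and the plan says "Given the repeated measurements on continuous outcomes, the data will be analyzed with mixed effects linear regression". BSS is collected at week 4, so a patient who leaves after that still contributes, and completers-only power overstates the loss. This stands, and it is why the point is minor. It is not a complete answer, because the same section also says "The key comparisons between treatment arms will assess changes from baseline to end of treatment" with approaches such as the t-test, and the plan's own allowance from 64 to 68 counts completers.

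A second objection is that the power figures rest on an inferred 45.75-point difference and on a baseline SD, since the document gives no SD of change. That is fair, and any restated power should come from the sponsor's own inputs. The patient count and the conflict between 5% and 10% do not depend on it.

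A third is that 5% is not an exact match either: 64 is a 5.9% loss, and 32/31 would also give about 80% power (79.8%, normal approximation). The accurate statement is that, of the two stated rates, 5% agrees with the 64 and the 68, and 10% does not.

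No reading rescues the 64 at 10%. The Time Line applies its rate to the 68 enrolled, and the Sample Size section sizes the groups from the same 68.

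**Conclusion.** The point holds, with minor weight. At 10% dropout, 68 enrolled leaves about 61 evaluable patients, so the stated 64 is about 3 too high. The 64, the 68 and the 80% power form a consistent set at 5%. The documents do not show which rate the investigators expect.

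If it is 10%, power falls by about 2 points, to about 78% (normal approximation) or 77% (t-test), and by up to about 2.5 points if all dropouts are in one arm. These figures assume a 45.75-point between-arm difference, SD 65 and completers only. The loss shrinks to the extent that the mixed model uses partial data. The Significance section presents the trial as a source of preliminary data for a larger one, which also keeps the weight low.

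**What to change.** State one dropout rate in the Time Line and Sample Size sections.

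- **If 5% is meant:** change the Time Line rate to 5%, with about 64 of the 68 patients remaining, and keep the 80% power.
- **If 10% is expected:** change the Time Line count to about 61, replace the 5% in the Sample Size section, and restate completers-only power (about 78% by the normal approximation, about 77% by t-test, on the reading above). State the between-arm difference and SD used, so that the figure can be checked.

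Either change is wording only, with no added patients and no change to design or analysis. Keeping 64 evaluable at 10% would instead mean enrolling 72, which is 4 more patients or 2 to 4 weeks at the stated rate of 1–2 per week. The sponsor could choose that, but it is not needed to remove the inconsistency.

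While editing, align the Study Procedures table, which gives the total as 66–68. At 66, 5% dropout leaves 66 × 0.95 = 62.7 and 10% leaves 66 × 0.90 = 59.4, so 64 would not hold at the lower end under either rate.

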#### **Study End-points**

Primary: Improvement in self reported overall Bowel Symptom Scores (BSS) after 8 weeks of treatment will be used as the primary endpoint.

Secondary:

- 1) Change in specific bowel symptoms: bowel frequency, bowel consistency, abdominal pain, urgency, and bloating after 8 weeks treatment.
- 2) IBS-QOL at end of treatment

*Definition of a Responder:* Patient who report at least 50% of the weeks of treatment with satisfactory relief (30% or more reduction in symptom) will be designated as responders.

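### The only BSS before treatment is taken at Visit 1, up to 8 weeks before dosing, so the primary change from baseline can span 16 weeks rather than 8

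*Combined protocol and SAP*

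**What the plan says.** - **When the BSS is collected.** The first-visit entry under Study visits reads "Questionnaires: BDQ, IBS-QOL, BSI-18, BSS, Nepean Dyspepsia Index (NDI". The other BSS collections are the week 4 mail or telephone contact and the fourth visit. The Study Procedures table agrees: its BSS row is marked at Visit 1, at 4 weeks and at Visit 4, and is blank at Visits 2 and 3.
- **How long before treatment.** Treatment Schedule states: "The patients will be consented and enter into the screening which can last up to 8 weeks". The first-visit list describes the same interval as a run-in: "Instructions to complete 2 week stool diary during 8-week run in period".
- **What happens at Visit 3.** Patients are randomised and study drug is dispensed. No questionnaire is listed. Drug may be mailed, in which case "they will be informed on dosing and storage of medication by telephone".
- **What the endpoint is.** Study End-points names improvement in the overall BSS, which "after 8 weeks of treatment will be used as the primary endpoint".
- **How baseline is used.** The statistical section says: "The key comparisons between treatment arms will assess changes from baseline to end of treatment". It does not define baseline. It also names mixed effects linear regression for the BSS, without saying how the pre-treatment score enters the model.

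**The concern.** A baseline for a treatment comparison should describe the patient when treatment begins. Here it may be 8 weeks old. The protocol itself expects symptoms to vary, since Study Procedures counts "progressive or non-fluctuating symptoms" among the red flags that call for colonoscopy. Two things are at stake.

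1. **Precision of the primary change score.** An older baseline may be less correlated with the week 8 score.
2. **Meaning of within-arm results.** The aim is described partly in before-and-after terms, and the trial is meant to supply preliminary data for a larger one. A change counted from Visit 1 includes whatever happened during screening. So does any 30% symptom reduction, the threshold in the responder definition, if it is counted from that score.

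**Working it through.** **Timing.** Up to 8 weeks of screening plus 8 weeks of treatment is 16 weeks, so up to 8/16 = 50% of the interval precedes the first dose. Eight weeks is a maximum, and the typical gap is not given.

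**The plan's sample size.** The inputs from the Sample Size section are mean 183, SD 65, a 25% change, 32 per group and two-sided alpha 0.05. The target difference is 0.25 × 183 = 45.75. The standard error is 65 × √(2/32) = 16.25, and 45.75/16.25 = 2.815. By the normal approximation, power is Φ(2.815 − 1.960) = 80.4%, and 80% power needs 31.7, so 32 per group. The plan's figure reproduces.

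**When an early baseline costs precision.** Let Y1, Y3 and Y8 be the BSS at Visit 1, at treatment start and at week 8, each with SD 65. Then

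- SD(Y8 − Y1) = 65 × √(2(1 − r18))
- SD(Y8 − Y3) = 65 × √(2(1 − r38))

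where r18 and r38 are the correlations with week 8. Precision is lost only if r18 is below r38. If they are equal, the loss is nil. With baseline as a covariate, the residual SD is 65 × √(1 − r²), which never exceeds 65.

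The documents give no correlation, so the values below are assumptions (32 per group, difference 45.75, normal approximation).

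| r | SD of change | Power, change score | Residual SD, adjusted | Power, adjusted |
|---|---|---|---|---|
| 0.3 | 76.9 | 66% | 62.0 | 84% |
| 0.4 | 71.2 | 73% | 59.6 | 87% |
| 0.5 | 65.0 | 80% | 56.3 | 90% |
| 0.6 | 58.1 | 88% | 52.0 | 94% |
| 0.7 | 50.3 | 95% | 46.4 | 98% |

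The cost of the early baseline is the difference between two rows, not the level of any one row. For example, if r38 were 0.6 and r18 were 0.5, power would be 80% instead of 88% with change scores, and 90% instead of 94% with adjustment.

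**A second illustration.** Take 65 as the SD of change from treatment start, and suppose screening drift is independent of later change, so that variances add.

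- Drift SD 10: √(4225 + 100) = 65.8, power 79.5%, 32.4 per group for 80% power.
- Drift SD 20: √(4225 + 400) = 68.0, power 76.8%, 34.7 per group.

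On these assumptions the loss is at most 80.4 − 76.8 = 3.6 points, or 34.7 − 31.7 = 3.0 patients per group.

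**Within-arm results.** Suppose a patient scores 183 at Visit 1 and drifts down 20 points (assumed) to 163 before dosing. A 30% reduction from Visit 1 means reaching 0.7 × 183 = 128.1. On treatment that takes a fall of 163 − 128.1 = 34.9 points, which is 34.9/163 = 21% of the score at treatment start.

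**The case against.** **The loss of precision is not shown.** This stands. If symptoms fluctuate around a stable level, drift before dosing tends to reverse later, so the independence assumed in the second illustration fails. A score at Visit 3 could then be just as noisy. SD 65 is also a cross-sectional baseline SD, and it equals the SD of change only when r = 0.5.

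**The effect depends on the model.** This also stands. The plan names mixed effects regression, and offers the t-test only as an example of a parametric approach. With the assumed inputs and covariate adjustment, the residual SD stays at or below 65, so power stays at or above the planned 80.4%.

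**The gap may be short.** Recent laboratory tests and endoscopy need not be repeated, so some patients could reach Visit 3 quickly. The protocol still allows the full 8 weeks.

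**The beginning could mean the start of treatment.** Treatment Schedule places the first BSS only loosely in time. But the visit list and the table both put it at Visit 1, and sites will follow those. The stool diary is a different instrument and cannot replace it.

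**A stated purpose might seem to be missed.** Treatment Schedule says the BSS is collected "to assess any change based simply on admission to the trial". A reader might infer that a run-in comparison was promised. The phrase is attached to all three BSS time points, and the placebo arm addresses such change between arms. It does not amount to a broken commitment.

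**Drug changes after Visit 1 might seem to distort the baseline.** This is possible, but the documents give no rate or size. The stable-regimen inclusion criterion and the exclusion for recent changes in gastrointestinal medication already limit it. The point does not rest on it.

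**Conclusion.** The timing gap is real. The only BSS that can serve as baseline may precede the first dose by up to 8 weeks, so the primary change can cover twice the interval that the endpoint names. That Visit 1 is the baseline is an inference, but no other score before treatment is scheduled.

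Two stronger readings are tempting, and the documents support neither. One is that the treatment comparison is biased. It is not, because the score is taken before randomisation and drift during screening is balanced between arms in expectation. The other is that the trial is underpowered for this reason, for example from the 66–73% rows in the table. Those rows follow from an assumed correlation of 0.3–0.4, and mostly reflect the separate matter of using a baseline SD for a change score.

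What remains is a possible loss of precision of unknown size, perhaps small or nil, and within-arm results that cannot separate screening drift from change on treatment. All power figures beyond the plan's own are illustrative. The point is worth raising as a cheap improvement, since a baseline not collected before dosing cannot be recovered later.

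**What to change.** Collect a BSS at Visit 3, or by mail or telephone just before it, completed before randomisation and before the first dose. State in the statistical section that this score is the baseline for the primary analysis. Where drug is mailed, the form must be returned or taken by telephone before the patient is randomised. The call about dosing may come after randomisation and would then be too late.

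Keep the Visit 1 BSS as the screening value and report the Visit 1 to Visit 3 change descriptively. Amend Treatment Schedule, the Study visits list and the Study Procedures table to match.

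The cost is one short questionnaire per patient (four symptom scales and an overall severity scale), 68 forms in all, plus a brief amendment. No extra visit is needed, since the week 4 BSS is already collected by mail or telephone. The planned sample size does not change.
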